3.4.2 Study Calendar

Study procedures are detailed in the study calendar, which is located on the following pages.

Examination	Screening ≤30 days before treatment initiation	First 60 days	Year 1 (after first 60 days) ± 3 days					Year 2 ± 3 days	Year 3 ± 1 month	Year 4 and Year 5
		Every 2 weeks	Monthly	At Day 90	Every 60 days	Every 90 days	End of cycle 13	Every 90 days	Every 6 months	At patient's routine visits
Informed consent	X									
Inclusion/exclusion criteria	X									
Vital signs	X									
Physical examination¹	X					X		X	X	
Medical History²	X									
Concomitant medication review	X	Continuous								
ECOG performance status	X									
Urine HCG test for applicable women only	X³	X³	X³					X³		
PET/CT¹⁴	X					X		X	X	
Hematology⁴	X	X	X					X		
Reticulocyte Count	X									
Chemistry⁵	X	X	X							
INR	X									
Fasting Cholesterol and Triglycerides	X		X							

Examination	Screening ≤30 days before treatment initiation	First 60 days	Year 1 (after first 60 days) ± 3 days					Year 2 ± 3 days	Year 3 ± 1 month	Year 4 and Year 5
Immunoglobulin panel (IGG, IGA, IGM)	X		X							
Hepatitis B and C screening ⁶	X ⁶									
HIV screening	X									
Bone marrow aspirate and biopsy ⁷	X			X ⁷			X			
Non-drug therapies and Blood transfusion record ⁸	X									
Research peripheral blood ⁹	X					X		X	X	
Study Drug Administration ¹⁰			Daily for 1 year							
Everolimus Serum trough levels ¹¹		X	X							
Rituximab ¹²						X				
Appropriate birth control measures			X ¹³							
Adverse events			Continuous							
Survival/Disease Status			Continuous							

¹ Should include a complete lymphomatous physical examination.

² History should try to document the pre high dose consolidative therapy MIPI score (age at diagnosis, ECOG performance status, LDH and WBC) and FLIPI score (age of diagnosis, LDH, ECOG performance status, number of extranodal sites, Ann Arbor stage) for Mantle and follicular lymphoma patients, respectively.

³ Urine HCG testing for applicable women conducted pre-study, every 4 weeks during everolimus administration until 8 weeks post everolimus administration.

⁴ Should include a heme 8 with differential

⁵ Chemistry should include a complete metabolic panel and glucose.

⁶ A detailed assessment of Hepatitis B/C medical history and risk factors must be done for all patients at screening, with testing performed prior to the first dose of everolimus. Please see section Addendums 8 and 9 for action to be taken for patients with positive baseline hepatitis B results and management of hepatitis reactivation.

⁷ Done at PI's discretion. When bone marrow biopsies are being performed, an additional 10 ml green top tube of aspirate will be collected for research samples.

⁸ All Concomitant medications/significant non-drug therapies taken \leq 30 days prior to the start and after start of study drug, including physical therapy and blood transfusions, should be recorded.

⁹ Collect 2-10ml green tops.

¹⁰ Bactrim SS PO qd or equivalent/suitable antimicrobial regimen for PCP prophylaxis during everolimus administration. Valtrex 500mg PO bid or acyclovir 400 mg PO tid for herpes prophylaxis in HSV/CMV positive individuals during everolimus administration. The initial dose of everolimus will be 10mg orally daily for a total of one year to maintain a target trough concentration between 3-15 ng/mL. Dose modification will occur as per Addendum 4. Treatment is to begin between six (6) weeks and ten (10) weeks after high dose consolidative therapy.

¹¹ Everolimus compliance will be monitored by serum blood analysis. Everolimus serum levels are commercially available through Quest Diagnostics (18883X) CPT code 80299, Mon-Fri. The target trough concentrations 3-15 ng/mL.

¹² Dose and schedule of Rituximab: 375mg/m² day +1 and then every 90 days for 1 year (a total of 4 infusions). Administration as per institutional standard. Rituxumab should only be given if patient's ANC > 1.5.

¹³ Patient must agree to use TWO acceptable versions of birth control monthly during everolimus administration and for 8 weeks after everolimus has been stopped.

¹⁴ PET/CT scans are recommended. If a PET/CT is not possible a CT of the chest, abdomen, and pelvis can suffice.

¹⁵ Years 4 and 5 of follow-up are for survival and disease status only and will occur at the patient's routine visits

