Genotoxicity studies covering relevant genotoxicity endpoints showed no evidence of clastogenic or mutagenic activity. Administration of everolimus for up to 2 years did not indicate any oncogenic potential in mice and rats up to the highest doses, corresponding respectively to 4.2 and 0.2 times the estimated clinical exposure. In reproduction studies, everolimus was toxic to the conceptus in rats and rabbits, and was considered potentially teratogenic in rats. It is therefore recommended that women of childbearing potential should use highly effective contraceptive measures during the entire treatment period and for 8 weeks thereafter. It is not known whether everolimus is excreted in human milk. In animal studies, everolimus and/or its metabolites were readily transferred into the milk of lactating rats. Therefore women who are taking everolimus should not breastfeed.

Everolimus Pharmacokinetics: Everolimus is rapidly absorbed with a median *t_{max}* of 1-2 hours. The steady-state *AUC_{0-τ}* is dose-proportional over the dose range between 5 to 70 mg in the weekly regimen and 5 and 10 mg in the daily regimen. Steady-state was achieved within two weeks with the daily dosing regimen. *C_{max}* is dose-proportional between 5 and 10 mg for both the weekly and daily regimens. At doses of 20 mg/week and higher, the increase in *C_{max}* is less than dose proportional. In healthy subjects, high fat meals reduced systemic exposure to everolimus 10 mg (as measured by *AUC*) by 22% and the peak plasma concentration *C_{max}* by 54%. Light fat meals reduced *AUC* by 32% and *C_{max}* by 42%. Food, however, had no apparent effect on the post absorption phase concentration-time profile.

The blood-to-plasma ratio of everolimus, which is concentration-dependent over the range of 5 to 5,000 ng/mL, is 17% to 73%. The amount of everolimus confined to the plasma is approximately 20% at blood concentrations observed in cancer patients given everolimus 10 mg/day. Plasma protein binding is approximately 74% both in healthy subjects and in patients with moderate hepatic impairment.

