Everolimus is a substrate of CYP3A4 and a substrate and moderate inhibitor of PgP. Following oral administration, everolimus is the main circulating component in human blood and is considered to contribute the majority of the overall pharmacologic activity. No specific excretion studies have been undertaken in cancer patients; however, data available from the transplantation setting found the drug to be mainly eliminated through the feces. There was a significant correlation between AUC_{0- τ} and pre-dose trough concentration at steady-state on the daily regimen. The mean elimination half-life of everolimus is approximately 30 hours.

1.1.3 Clinical Experience with Everolimus: Everolimus has been in clinical development since 1996 as an immunosuppressant in solid organ transplantation and was approved in Europe in 2003 under the trade name Certican®, for the prevention of organ rejection in patients with renal and cardiac transplantation. Additional non-oncologic indications currently being explored are wet age-related macular degeneration (AMD) and autosomal dominant polycystic kidney disease (ADPKD).

In oncology, everolimus has been in clinical development since 2002 for patients with various hematologic and non-hematologic malignancies as a single agent or in combination with antitumor agents. Malignancies that are currently being evaluated in Novartis sponsored studies include the following: metastatic renal cell carcinoma (mRCC), breast cancer, gastroenteropancreatic neuroendocrine tumors (GEP-NET), mantle cell lymphoma and diffuse large B cell lymphoma (DLBCL), hepatocellular cancer (HCC), gastric cancer, and lung cancer. In addition, treatment of patients with Tuberous Sclerosis Complex (TSC) associated subependymal giant cell astrocytoma (SEGA) and Angiomyolipoma is also being evaluated.

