3.3.1 Everolimus administration

The initial dose of everolimus will be 2.5mg orally daily for a total of one year to maintain a target trough concentration between 3-15 ng/mL

Everolimus should be administered orally once daily, preferably in the morning, at the same time every day with or without food.

Everolimus tablets should be swallowed whole with a glass of water.

The tablets must not be chewed or crushed.

If vomiting occurs, no attempt should be made to replace the vomited dose

Everolimus will be provided by Novartis. Everolimus is formulated as tablets for oral administration of 2.5mg, 5mg, and 10mg strength.

Dose modification will occur as per Addendum 4.

Everolimus can still be administered per protocol even if Rituximab treatment is on hold.

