3.4 Visit schedule and assessments

3.4.1 Visit schedule: Examination and Laboratory evaluations

Physical examination: Complete lymphomatous physical examination every ninety (90) days for the first two (years), then every six (6) months for the third year.

CBC with platelet count every two (2) weeks for the first sixty (60) days then monthly for a total of one (1) year, then every 90 days for the next two (2) years.

Metabolic panel every two (2) weeks for the first sixty (60) days then monthly for a total of one (1) year

Imunoglobulin panel (IgG, IgA, IgM), fasting triglycerides and fasting cholesterol levels monthly for a total of one (1) year.

Patients will be scheduled for an IVIG infusion if their IgG level falls below 500 mg/dL.

Patients with an IgG serum level of <500mg/dL will either have supplemental Ig administration or changes in primary oral antimicrobial prophylaxis per PI discretion.

HCG urine pregnancy testing every 4 weeks during everolimus administration and for 8 weeks post everolimus administration for women of child bearing potential

Everolimus serum trough levels every two (2) weeks for the first sixty (60) days then monthly for a total of one (1) year. Everolimus levels will not be drawn during a hold once the level is less than 1.0.

Research peripheral blood labs (2 green top tubes) every ninety (90) days for a total of three (3) years.

Bone marrow evaluation at ninety (90) days and at the end of cycle 13 (or the 365 day appointment when patients move into the follow-up stage) at PI's discretion. If a bone marrow evaluation is performed, an additional 10 ml green top tube of aspirate will be drawn for research purposes.

Adverse events and concomitant medications will be monitored throughout the duration of the study.

Survival/disease status will be assessed at year 4 and year 5.

Radiographic evaluation

Computerized Tomography (CT) of chest/abdomen/pelvis and whole body Positron emission tomography (PET) scanning every ninety (90) days for two (2) years, then every six (6) months for the third year.

CT scans of the neck and other structures as determined by physical examination

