6.0 Statistical Considerations

This is a study of maintenance rituximab with mTor inhibition (everolimus) after high-dose consolidative therapy in CD20+, B-cell Lymphomas and Hodgkin's Lymphoma. It is hypothesized that the addition of new agents in patients with minimal residual disease will improve event free survival and that everolimus may act synergistically with rituximab.

Primary Objective:

To determine the safety of maintenance rituximab and prolonged mTOR inhibition with everolimus in CD20+, B cell lymphoma and Hodgkin's Lymphoma after high-dose consolidative therapy.

Secondary Objectives:

1. The secondary endpoint of this study is to evaluate event-free survival (EFS) at three years. EFS is defined as the interval from registration to the date of first objective disease progression, death from any cause, or last patient evaluation. Patients who have not progressed or died will be censored at the last date they were assessed and deemed relapse-free.
2. To determine whether maintenance rituximab with everolimus treatment reduces the frequency circulating cancer cells.
3. To determine if relapsed disease is sensitive, in-vivo, to mTor kinase inhibition.

Study Design:

Treatment will consist of rituximab 375mg/m² q 90 days (4 infusions) with everolimus 2.5 mg orally daily for one year. There will be no drug escalation in this study however serum drug levels will be monitored and the level of everolimus will be maintained in the therapeutic window. For patients outside the range of 3 – 15ng/mL and not experiencing grade 3 or higher toxicity, the dose will either be increased or decreased by 2.5mg per day to bring patients within range, down to 2.5 mg every 4 days. Addendum 4 provides details on dose adjustments and treatment holds. For patients experiencing grade 3 or higher toxicities adjustments will be made as detailed in addendum 4. The study will be monitored continuously for safety.

Sample size/Accrual Rate:

The accrual rate for this study is expected to be 20 patients per year. The safety objective of this trial is based on the precision of estimating grade 3 or higher toxicities. Sixty patients will allow us to estimate the proportion of patients experiencing grade 3 or higher toxicities with a precision of $\pm 13\%$.

Early Stopping Guideline for Safety:

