Reference: Internal Clinical Pharmacology Drug-drug interaction (DDI) memo, updated Oct. 2, 2011, 29-Oct-2012 which summarizes DDI data from three sources including the FDA's "Guidance for Industry, Drug Interaction Studies", the University of Washington's Drug Interaction Database, and Indiana University School of Medicine's Drug Interaction Table.

Addendum 4: Dose Modifications for abnormal serum drug concentrations without grade III/IV toxicities, grade \geq III toxicities (CTCAE version 4.0) except for stomatitis and lipid/hyperglycemia toxicities

- Patient will have regularly scheduled everolimus levels drawn throughout the study
- Everolimus is available in 2.5mg, 5mg and 10mg strengths
- The reference range for patients experiencing a <II common toxicity (CTCAE version 4.0) is 3-15ng/mL
- Anytime a dose is adjusted, repeat everolimus serum trough levels will be re-drawn 14 days (\pm 3 days) later. As clinically possible, all patients' other labs will be reset to match this new everolimus serum trough level schedule.
- Once everolimus is held due to high serum trough levels, everolimus should be held for 7 days before restarting at a lower dose level.
- During a treatment hold, everolimus levels will not be drawn once the serum trough level is less than 1.0.
- There is no limit on how long a patient can be on everolimus treatment hold. Labs will be monitored every two weeks while the patient is on hold.
- For patients >15 ng/mL or <3.0 ng/mL and not experiencing >II grade common toxicity, their dose will be adjusted by $+/-.2.5$ mg/day; lowest dose allowed is 2.5mg every 4 days. The study nurse will provide a calendar to patients when the dose level is 2.5 mg taken every 3 or 4 days
- If a patient on a schedule of 2.5 mg (QOD) or lower misses a dose, that dose should be made up.
- Non-hematologic grade \geq III CTCAE toxicities: hold drug until CTCAE toxicity is (I) but can be continued at grade 2 if the baseline values were within the range of grade 2 and restart at a dose level -2.5mg/day. Lowest dose allowed is 2.5mg every 4 days
- Grade 4 or 4 clinical failure – discontinue RAD001
- Recurrence of grade 4 toxicity after dose reduction – discontinue RAD001
- Hematologic grade \geq III CTCAE toxicity
 - Anemia
 - Hgb <8.0 g/dL: transfuse RBC; hold drug for 7 days or until Hgb >10 mg/dL (untransfused): whichever is longer. Restart at a dose - 2.5mg/day. Lowest dose allowed is 2.5mg every 4 days
 - Thrombocytopenia

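### Study calendar footnote 10 starts everolimus at 10 mg daily, four times the 2.5 mg daily in Sections 3.3.1 and 6.0

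*Combined protocol and SAP*

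**What the plan says.** Three current passages state the starting dose.

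- **Section 3.4.2, footnote 10**, to which the Study Drug Administration row points: "The initial dose of everolimus will be 10mg orally daily for a total of one year to maintain a target trough concentration". The calendar is introduced with "Study procedures are detailed in the study calendar", and the same footnote carries the prophylaxis instructions and the treatment-start window.
- **Section 3.3.1**: "The initial dose of everolimus will be 2.5mg orally daily for a total of one year to maintain a target trough concentration".
- **Section 6.0, Study Design**: rituximab "with everolimus 2.5 mg orally daily for one year".

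All three aim for a trough of 3-15 ng/mL. Addendum 4 gives the trough rule: "For patients >15 ng/mL or <3.0 ng/mL and not experiencing >II grade common toxicity, their dose will be adjusted by" 2.5 mg/day up or down. Section 3.4.1 schedules "Everolimus serum trough levels every two (2) weeks for the first sixty (60) days", then monthly to one year.

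On the minor point, Section 6.0 defines a safety failure partly as intolerance of 2.5 mg every other day and calls that the minimum. It does so in both the early stopping guideline for safety and the analysis of the primary objective. The Study Design text in the same section, and Addendum 4, set the lowest permitted dose at 2.5 mg every 4 days.

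**The concern.** The calendar is what site staff are likely to work from, and nothing about 10 mg would alert them. It is a supplied tablet strength and the daily dose used in the relapsed lymphoma studies summarised in Section 1.1.3. Treatment starts 6 to 10 weeks after high-dose therapy, and the primary objective is safety.

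A mixture of starting doses would also blur the safety results. The primary analysis reports the proportions of patients needing dose changes down and up, and both depend directly on the starting dose. So does the distance to the failure threshold. Taking every other day as the step below 2.5 mg daily, a 10 mg starter passes through four reductions to reach it (7.5, 5, 2.5 daily, then every other day). A 2.5 mg starter needs one.

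**Working it through.** The plan states no figure for this point, so the check sets the dose texts side by side and follows the adjustment rule from each start.

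**Size of the conflict**

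- Ratio: 10 / 2.5 = 4.
- Weekly dose: 10 × 7 = 70 mg against 2.5 × 7 = 17.5 mg.
- Dose taken by the first scheduled on-treatment trough at week 2, if none is held: 10 × 14 = 140 mg against 2.5 × 14 = 35 mg.

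**Does the trough rule bring the two starts together?** The window is 15 / 3 = 5-fold wide, and the doses differ 4-fold, so both can be in range for one patient. To go further, assume trough is proportional to dose. Section 1.1.2 gives partial support: steady-state AUC "is dose-proportional over the dose range between 5 to 70 mg in the weekly regimen and 5 and 10 mg in the daily regimen", and AUC correlates with "pre-dose trough concentration at steady-state on the daily regimen". Proportionality of the trough itself, and its extension down to 2.5 mg, are assumptions.

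Let T be a patient's trough at 10 mg daily, so the trough at dose d is T × d / 10. Take 3 ≤ T ≤ 15 and no other reason to change dose. A 10 mg starter stays at 10 mg. A 2.5 mg starter steps up until the trough reaches 3 ng/mL:

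- At 2.5 mg the trough is T/4, which is at least 3 when T ≥ 12.
- At 5 mg it is T/2, which is at least 3 when T ≥ 6.
- At 7.5 mg it is 0.75 T, which is at least 3 when T ≥ 4.

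| T (ng/mL at 10 mg) | Settles at, from 10 mg | Settles at, from 2.5 mg | Ratio |
|---|---|---|---|
| 3 to <4 | 10 mg | 10 mg | 1 |
| 4 to <6 | 10 mg | 7.5 mg | 1.33 |
| 6 to <12 | 10 mg | 5 mg | 2 |
| 12 to 15 | 10 mg | 2.5 mg | 4 |

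Under the same assumption, anyone with T from 3 to <12 needs an upward change from 2.5 mg and none from 10 mg, so the reported adjustment proportions shift with the start.

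If troughs at 10 mg are too high, correction is slow. Going from 10 to 2.5 mg takes (10 − 2.5) / 2.5 = 3 steps. With a repeat trough 14 days after each, that is about 42 days, and only if every trough on the way exceeds 15 ng/mL.

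**Effect on the statistical design.** The Section 6.0 safety figures do not use the dose. The 95% half-width at n = 60 is 1.96 × √(0.25/60) = 12.7%, against the stated 13%. The printed stopping boundaries are reproduced for every n from 2 to 60 from the beta(1, 6) prior and the 75% posterior rule. They stand whichever starting dose is right.

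**Minor point.** Every other day is 2.5 × 7 / 2 = 8.75 mg per week; every 4 days is 2.5 × 7 / 4 = 4.375 mg per week. The dose called the minimum is twice the real one. Read literally, a patient who cannot tolerate every-other-day dosing but continues on a permitted every-3- or every-4-day schedule counts as a failure.

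**The case against.** The best reply is that the intent is plain. The section on everolimus administration and the Study Design text both say 2.5 mg, the calendar row itself says only that dosing is daily for a year, and 10 mg appears as the starting dose in one footnote. Harm needs someone to dose from that footnote, and the documents do not show which text dosing orders follow.

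There are also safeguards besides the trough rule. Blood counts and chemistry are checked every two weeks for 60 days, and Addendum 4 requires holds for most toxicities of grade 3 or higher. Addenda 5 and 7 act on some grade 2 events, and Addendum 1 halves the dose with moderate CYP3A4 or PgP inhibitors.

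Section 1.1.3 describes 10 mg daily as well tolerated in heavily pretreated patients. It also reports grade 3 thrombocytopenia in 30% of that group, and dose reductions or delays in 10 of 19 patients with relapsed Hodgkin's disease. These groups have no 2.5 mg comparator and were not treated after consolidation, so they are only indicative.

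Much of this stands: 2.5 mg is the likely intent, the safeguards limit harm, excess risk from the error cannot be estimated, and the settling-dose table rests on an assumption. None of it removes the contradiction. No sentence ranks the passages, and the toxicity safeguards act after exposure. An in-range patient without toxicity or an interacting drug is not moved to the lower dose.

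On the minor point, a failure threshold above the protocol floor is coherent and may be deliberate. Only the word minimum conflicts.

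**Conclusion.** The concern holds, and the footnote must be corrected. As written, the protocol gives two starting doses of the investigational drug that differ by a factor of 4, both in current operational text. That factor needs no assumption.

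For patients in range at 10 mg, the lasting difference is 1- to 4-fold. This assumes trough proportional to dose down to 2.5 mg and no dose change for toxicity or interacting drugs. The documents give no trough distribution, so the number of patients affected is unknown.

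No sample size, stopping boundary or operating characteristic changes. The grade rests on the starting dose alone; the minimum-dose wording is a minor clarification of the primary safety event.

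**What to change.** Have the sponsor confirm the 2.5 mg daily start, then change 10 mg to 2.5 mg in footnote 10 so that it matches Sections 3.3.1 and 6.0. Section 3.2.5 shows that some patients had already been dosed under earlier protocol versions, so it is worth checking which start enrolled patients received.

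For the minor point, amend both places in Section 6.0 that define the failure event. Either refer to the lowest dose in Addendum 4, or drop the word minimum and state that every other day is the intended, stricter threshold.

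The cost is a wording amendment: one number in a footnote and one phrase in two places. It needs no new visits, sample size or stopping boundary.
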